3. BACKGROUND AND RATIONALE

Malaria elimination has been undertaken in the Western Greater Mekong Subregion (Western Thailand, Eastern Myanmar) in an attempt to prevent the spread of artemisinin- and multidrug resistant falciparum parasites.

The malaria elimination task force (METF) has been operating in Eastern Kayin State since April 2014. METF is present in the four townships of Hapun, Hlaingbwe, Myawaddy and Kawkareik, in a total of 158 village tracts. METF is providing access to early diagnosis and treatment of malaria in 1200 villages through community-based facilities “Malaria Posts” (MP) [1]. The monitoring of falciparum malaria incidence in the villages after the opening of a MP showed that incidence decreases quickly in most locations (approximately by 25% per quarter of MP activity, Figure 1A). As a result in April 2017 a total of 965 villages out of 1,222 villages (79%) corresponding to 104 village tracts were free of *P. falciparum* malaria for at least 6 months.

However the activity of the MP had more limited impact in villages with high prevalence of asymptomatic infections: a slower or no decrease of falciparum was observed, even after >24 months of MP activity (Figure 1B).

[figure not shown]

Figure 1: Malaria incidence (falciparum in red and vivax in black) since MP opening in the townships of Hapun (n=468 MP) and Myawaddy (n=100) where hotspots were identified (52/69 located in Hapun Township, 7/69 in Myawaddy). Different y-scales are used in each graph.

A: non-hotspot villages. The widening confidence intervals after 24 months indicate that fewer MP have been active for 2 years or more. The oscillations in *P. vivax* incidence are related to seasonal peaks occurring in the same locations in Myawaddy Township.

B: hotspot villages, without intervention. Only 16 hotspots contribute to follow-up for durations of MP activity above 18 months. These high incidence locations were only identified during the final campaign of baseline surveys (Nov. 2016 to Jan. 2017) and had not been addressed by April 2017. The median duration of MP activity before intervention was 12 months (IQR=5-16). Over the period corresponding to a duration of MP activity between 0 and 18 months, a decrease can be observed in hotspots which is captured by the statistical model.

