Following a successful pilot study initiated in 4 villages in 2013 [2], METF has conducted surveys to measure the prevalence of asymptomatic malaria infections. Villages with high prevalence of malaria (>40%) in which falciparum represented at least 20% of malaria infections, were defined as hotspots and treated with a 3-month mass drug administration campaign. These campaigns were very successful at depleting the reservoir of asymptomatic carriage of *P. falciparum* (Figure 2), which translated in a significant decrease in clinical episode incidence (Figure 3). In spite of its success, this strategy is difficult to scale up due to numerous constraints and was not considered by the Myanmar NMCP. However, the successful decrease in case incidence obtained by treating the reservoir of asymptomatic carriers sparks interest for a simpler and faster intervention, relying on mass screening and treatment (MSAT) rather than MDA (Table 1). Such approach was previously impossible due to the lack of sensitivity of standard RDT to detect asymptomatic infections. A newly available ultrasensitive RDT (URDT) shows a 50% sensitivity and 99% specificity compared to uPCR. This sensitivity is sufficiently high to allow accurate detection of high prevalence villages, and to warrant evaluation of the impact of a URDT-based screening and treatment intervention. MSAT is a method approved by the Myanmar NMCP and recommended by the WHO.

[figure not shown]

Figure 2: Impact of MDA on *P. falciparum* prevalence (95% confidence interval) comparing baseline and 12 months after MDA (n=40 villages) in villages equipped with MP and addressed with MDA between January 2015 and April 2016.

By design, an MSAT intervention using a field test will not identify all carriers. However, it is likely to decrease village level prevalence by 50%, and parasite biomass by >97%, since 87% of infections with parasite densities >1000 parasite/mL are expected to be identified. This depletion of the reservoir could be sufficient to durably modify the village-level transmission and initiate or accelerate the MP-driven decrease. Additionally, a URDT-based MSAT strategy could be an extremely useful tool to respond to malaria outbreaks. Indeed, by rapidly screening the population of a village where the incidence has reached alarm thresholds, parasite carriers could be rapidly identified and treated, leading to a rapid decrease in the reservoir and an interruption of the transmission.

[figure not shown]

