5. STUDY DESIGN

Stepped-wedge open-label, non-randomized, cluster intervention.

This study will be performed in clusters (hamlet (isolated group of household, village, or group of village). The intervention will be conducted in two types of clusters, both corresponding to locations where an excess of case was detected.

Group 1: Sustained high incidence clusters, characterized by a yearly cumulative incidence >84 cases/1000/year

Villages in group 1 will be attributed an intervention a given year based on the cumulative incidence over the previous 12 months (METF stratification January, including the last 2 transmission seasons). The order of intervention will be decided based on logistic constraints and highest incidence.

Group 2: Focal transmission clusters, corresponding to locations where an epidemic alert has been signalled and confirmed (see definition of thresholds).

*Villages in group 2 will be attributed an intervention based on *P. falciparum* incidence in the previous 4 weeks. In near-0 transmission area, an intervention will be conducted in each likely source location of transmission of a locally acquired case. In the other areas (METF1+METF2), the intervention will be triggered when the incidence is above the pre-defined epidemic threshold.*

In each cluster, all inhabitants will be invited to undergo an URDT test to identify their infection status, and will receive the appropriate treatment according to their characteristics. Information on village inhabitants absent during the MSAT activities will be obtained from village population lists provided by the village headman and from household member declarations. During the URDT screening, all individuals will receive a unique identifying number that will be used to record demographic data in the MSAT paper logbook and to label URDT and reference sample.

Before and after MSAT intervention, incidence of clinical malaria episodes will be recorded at the MP (1 or several) serving the cluster receiving the intervention. No individual data will be collected to link clinical case participation, infection status and incidence of clinical episodes.

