6.1.1. Group 1: sustained high incidence villages

Villages classified as high incidence, low probability of elimination (*P. falciparum* cumulative incidence >84 cases/1000/year, in spite of >1 year of functioning malaria post) will be eligible to be included in group 1. Villages in this group will be addressed by MSAT waves of 10-15 villages.

Villages will be included in a given wave based on accessibility to the team and proximity from each other, as well as requirements for the program impact. Wave 1 will include 5 villages and be conducted during first semester 2018, after which a maximum of two waves will be conducted per semester.

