9.2.3. Sample size for retrospective incidence comparison between MSAT and MDA

If comparing 50 MSAT villages and 50 MDA, we will be able to differentiate MSAT from MDA efficacy if MSAT achieves around 50% of MDA impact on incidence or less.

The average village size was 190 inhabitants (coefficient of size variation=0.64) with an intra-cluster correlation coefficient of 0.12 (estimated using incidence series) and MDA was already completed in 60 villages. The 10 villages in which MDA was conducted based on prevalence values that will be the furthest

from what will be measured during the MSAT campaign will be excluded. Villages receiving MSAT after MDA will be excluded from MSAT group. With a comparison of 50 MSAT, it will be possible to detect a difference in incidence rate of 50/1000/year between the two groups (with alpha=5% and power=80%). This would correspond to a reduction of incidence by only 40% after MSAT (70 cases/1000/year after compared to 125 before). With MDA, 80% incidence reduction was achieved: the average cumulative incidence during the first year after MDA was 20 case/1000/year, compared to 125 before.

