9.3. Analysis of Outcome Measures

Primary outcome: stepped-wedge comparison of incidence.

The incidence comparison will be conducted over a 2-year series of weekly incidence data, corresponding to 12 months before and 12 months after MSAT intervention. A generalized additive multilevel mixed model will be used to adjust for location, season, and temporal trend due to MP activity using uni-(seasonality, duration of MP activity in the village) or bivariate (latitude and longitude) splines, including random intercept and slopes at village level. MSAT intervention will be included in the model as a 0-1 variable. The incidence rate ratio obtain for this variable will quantify the average decrease in incidence after MSAT campaign compared to before.

Secondary outcome: before-after comparison of prevalence

For each village, the fractional change in prevalence before MSAT and 12 months after will be calculated and compared to 0% change. This change will be compared to the fractional change observed after MDA.

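### Section 9.3 compares prevalence falls after MSAT and MDA unadjusted, although the villages were selected differently and probably measured on different assays; the selection difference probably favours MDA

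*Combined protocol and SAP*

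**What the plan says.** For the prevalence outcome, section 9.3 states: "For each village, the fractional change in prevalence before MSAT and 12 months after will be calculated and compared to 0% change". It then adds: "This change will be compared to the fractional change observed after MDA". It names no test, covariate or matching. The objectives table in section 4 places the MSAT-MDA comparison, on both prevalence and incidence, under tertiary objectives and calls it retrospective.

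The two sets of villages come from different rules.

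- **MDA (section 3):** "Villages with high prevalence of malaria (>40%) in which falciparum represented at least 20% of malaria infections, were defined as hotspots", and these were then treated. Section 9.2.3 confirms that MDA was allocated on measured prevalence.
- **MSAT group 1 (section 5):** "Villages in group 1 will be attributed an intervention a given year based on the cumulative incidence over the previous 12 months". Section 6.1.1 sets the threshold: "cumulative incidence >84 cases/1000/year, in spite of >1 year of functioning malaria post". Prevalence at M0 is measured during MSAT (section 4), after the village has been selected.

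The only comparability step is in section 9.2.3, which drops MDA villages: "The 10 villages in which MDA was conducted based on prevalence values that will be the furthest" from the MSAT values. It is written for the incidence comparison.

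**The concern.** A village chosen because a survey gave a high value will tend to give a lower value next time, even if nothing is done. If the change is measured from that same survey, part of the fall reflects selection. MDA villages were selected on surveyed prevalence. MSAT villages are selected on another variable, and their baseline prevalence is a later, separate measurement. The two fractional changes therefore carry different amounts of regression to the mean.

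The measuring scale is a second difference. The MDA rule needs total malaria prevalence and the falciparum share. A falciparum-only HRP2 test cannot supply these, and section 3 describes the URDT as newly available. MSAT prevalence is measured by URDT and Quansys ELISA (sections 4 and 7.7). An imperfect test changes the size of a fractional fall, so equal true effects can read differently.

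At stake is a ranking of MSAT against MDA that partly reflects how villages were chosen and tested.

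**Working it through.** **1. The plan's own figure.** Section 9.2.2.2 uses 16% falling to 8%, 60 samples per cluster, ICC 0.15, alpha 0.05 and power 0.80. The two-proportion formula gives 258 per period. The design effect is 1 + 59 × 0.15 = 9.85, and 258 × 9.85 / 60 = 42.4, rounded up to the stated 43 clusters. This reproduces, but covers only the MSAT before/after comparison. No power is given for MSAT against MDA on prevalence.

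**2. Is the MDA selection survey also the baseline?** The Figure 2 caption describes MDA results as "comparing baseline and 12 months after MDA (n=40 villages". The Figure 1B caption says of hotspots: "These high incidence locations were only identified during the final campaign of baseline surveys (Nov. 2016 to Jan. 2017". Together with the selection rule, this makes a shared survey likely. No sentence says so, and the Figure 1B wording concerns a later campaign than the MDAs in Figure 2 (January 2015 to April 2016).

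**3. Regression with no true effect.** The documents do not give the MDA survey size, the spread of village prevalence or its year-to-year correlation r. Assumed: 50-150 people surveyed per village; mean falciparum/vivax prevalence 5%/15% or 10%/20%; ICC 0.10-0.15; r = 1.0 or 0.8. The MDA rule was simulated as written (total above 40%, falciparum share at least 20%), comparing the selecting survey with a re-survey. For MSAT, the same fraction of villages was selected on an incidence proxy with correlation 0.4-0.8 to prevalence, followed by a separate M0 survey of 150 people.

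| Pf/Pv mean, ICC | r | Apparent MDA fall (n = 150 to 50) | Apparent MSAT fall | Excess, points |
|---|---|---|---|---|
| 5%/15%, 0.15 | 1.0 | 3.1-8.6% | 0% | 3-9 |
| 5%/15%, 0.15 | 0.8 | 25.7-29.8% | 15-22% | 3-15 |
| 10%/20%, 0.10 | 1.0 | 3.4-9.4% | 0% | 3-9 |
| 10%/20%, 0.10 | 0.8 | 17.0-21.7% | 8-14% | 3-13 |

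The excess was positive in every setting run for both sets. Over a wider grid for MDA alone, the apparent fall was about 2-12% at r = 1.0 and 17-31% at r = 0.8.

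**4. Regression with a true effect D.** If R is the fall with no effect, the apparent fall is 1 - (1 - R)(1 - D). For D = 80%, R = 5% gives 1 - 0.95 × 0.20 = 81%, and R = 30% gives 1 - 0.70 × 0.20 = 86%, so 1-6 points are added. For D = 50%, R = 10% gives 55% and R = 30% gives 65%. If D is equal in both sets, the between-set excess shrinks by the factor (1 - D): at 80%, 3-15 points become 0.20 × 3 = 0.6 to 0.20 × 15 = 3 points.

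**5. Assay scale.** Appendix D gives ELISA sensitivity 83.0% and specificity 96.1% against uPCR, a false-positive rate of 3.9% (58/1485). Excluding the 26 with Plasmodium DNA leaves 32/1485, about 2.2%. Observed prevalence is 0.83p + (1 - p) × FP. The 16% start is the section 9.2.2.2 assumption; the 80% fall is illustrative.

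- FP 2.2%: 16% reads 0.1328 + 0.0185 = 15.1%; 3.2% reads 0.0266 + 0.0213 = 4.8%; the fall reads 68%.
- FP 3.9%: 16% reads 0.1328 + 0.0328 = 16.6%; 3.2% reads 0.0266 + 0.0378 = 6.4%; the fall reads 61%.

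A test on the uPCR scale would read 80%. Section 7.9 itself treats the scales as different, equating 5% by URDT with 7.5% by uPCR.

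**The case against.** Several points on the other side stand.

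- **MSAT villages regress too.** They are selected on a high preceding 12 months, and incidence is related to prevalence. The issue is unequal regression.
- **Selection on falciparum is partial.** The MDA rule acts on total malaria and on the falciparum share. The simulation allows for this.
- **The bias is small if MDA works very well.** Step 4 shows this.
- **The shared survey and the MDA assay are inferences.** No section states either.
- **The comparison is tertiary and retrospective.** No sample size or decision rule for prevalence rests on it.

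A reader might infer a much larger bias from (1 - r)(1 - mu/p0), which gives 5-33% with a selected-village mean p0 of 16%, an overall mean mu of 3-8% and r of 0.6-0.9. The documents do not support that as the size of the problem. It is the no-effect fall in MDA villages alone, its 16% is the plan's figure for group 1 MSAT villages, and it assumes selection directly on falciparum prevalence. A reader might also infer that this comparison will decide whether MSAT replaces MDA. Section 3 says only that MDA is hard to scale up and was not considered by the national programme, while MSAT is already approved.

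None of this supplies the missing adjustment. The additive mixed model in section 9.3 is for incidence, as is the exclusion of 10 villages. Extending that exclusion to prevalence would match on the same noisy baseline and would not remove the regression.

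**Conclusion.** The concern holds in a limited form. As written, the MSAT-MDA prevalence comparison sets raw fractional changes against each other when the two sets of villages were selected on different variables. Regression to the mean probably favours MDA, by about 3-15 points with no true effect. At a true 80% fall it adds about 1-6 points to the MDA figure. These sizes rest on the assumed inputs in step 3 and on the MDA selection survey being the baseline.

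The assay difference is separate and could be larger: 12-19 points at a true 80% fall from 16%, if MDA was read on a uPCR-like scale and MSAT by ELISA. Because the MDA assay is not named, neither its size nor its direction is established. The before/after MSAT result and the 43-village calculation are not in question. This is a cheap correction to a tertiary comparison.

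**What to change.** In section 9.3, replace the comparison of raw fractional changes with the following.

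1. Model 12-month falciparum prevalence (positives out of tested, village random effect) on intervention type. Adjust for baseline falciparum prevalence and for incidence per week of MP activity before the intervention, using the history available up to 12 months.
2. Name the MDA assay. Put both baseline and M12 prevalence, in both sets, on one assay scale with Appendix D error rates and a sensitivity range. Rescaling only the baselines is not enough: with an equal true fall from 16% to 3.2%, M12 would read 3.2% by a uPCR-like test and 4.8-6.4% by ELISA, an odds ratio of about 1.5-2.1 against MSAT.
3. Restrict to villages that overlap in baseline falciparum prevalence and prior incidence. Overlap in total malaria prevalence cannot be required, because the MSAT tests do not measure it.
4. If the MDA assay cannot be aligned, or the overlap is too small, show the two changes side by side as descriptive, state the selection and assay differences, and give no test or efficacy ranking.

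The cost is plan wording and one model. Some villages will drop out through non-overlap or short history: the Figure 1B caption gives a median of 12 months of MP activity before intervention (IQR 5-16), so about half of the hotspots have less than a full year. The comparison becomes less precise, and adjustment can only deal with the selection variables that were recorded in both sets.

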10. DATA MANAGEMENT

10.1. Access to Data

Direct access will be granted to authorised representatives from the Shoklo Malaria Research Unit/Mahidol Oxford Research Unit and any host institution for monitoring and/or audit of the study to ensure compliance with regulations.

10.2. Data Handling and Record Keeping

All data collected specifically for the study (MSAT logbook, AE forms and where appropriate, follow-up survey logbook, demographic follow-up and individual falciparum clinical case data) will be recorded on paper forms in the field and entered in a secure Access database managed by SMRU data management team.

Laboratory results will be merged to this database using patient unique identifier which will be used to label the samples.

Analysis will be conducted on anonymized data.

11. QUALITY CONTROL AND QUALITY ASSURANCE PROCEDURES

The study will be conducted in accordance with relevant regulations and standard operating procedures.

12. ETHICAL AND REGULATORY CONSIDERATIONS

12.1. Declaration of Helsinki

The Investigator will ensure that this study is conducted in accordance with the principles of the Declaration of Helsinki.

12.2. Guidelines for Good Clinical Practice

The Investigator will ensure that this study is conducted in accordance with relevant regulations and with Good Clinical Practice.

12.3. Approvals

The protocol, informed consent form, and participant information sheet will be submitted to the Ethics Review Committee on Medical Research Involving Human Subjects from the Republic of the Union of Myanmar, Ministry of Health and Sports, Department of Medical Research (Lower Myanmar), OXTREC for written approval. Furthermore, the protocol, informed consent form, and participant information sheet will be reviewed by community-based committees assembling members of the communities in which the study will be performed: the Karen Department of Health and Welfare and the Tak Community Advisory Board [8].

The Investigator will submit and, where necessary, obtain approval from the above parties for all amendments to the original approved documents.

12.4. Participant Confidentiality

The study staff will ensure that the participants' anonymity is maintained. The participants will be identified only by a participant ID number on all study documents and any electronic database, with the exception of the MSAT logbook, where participant name will be added to allow identification. All documents will be stored securely and only accessible by study staff and authorised personnel. The study will comply with the Data Protection Act, which requires data to be anonymised as soon as it is practical to do so.

12.5. Expenses and Benefits

No payments will be given to participants for their participation in the study.

12.6. Reporting

The CI shall submit an Annual Progress Report to OxtREC on the anniversary of the date of approval of the study. In addition, the CI shall submit an End of Study Report to OxtREC within 12 months of completion of the study.

13. FINANCE AND INSURANCE

13.1. Funding

This project is funded by a grant from the Bill & Melinda Gates Foundation to the Shoklo Malaria Research Unit, via Oxford University and the Mahidol Oxford Research Unit.

13.2. Insurance

The project is covered under the Oxford University sponsorship.

The University has a specialist insurance policy in place which would operate in the event of any participant suffering harm as a result of their involvement in the research (Newline Underwriting Management Ltd, at Lloyd's of London).

14. PUBLICATION POLICY

The results of this study will be published in peer-reviewed journal, following the standard policy of the Mahidol-Oxford University Research Unit.

[figure not shown]
The results will be communicated to the communities, by the Community Engagement team of the Malaria Elimination Task Force.

16. APPENDIX A: STUDY FLOW CHART

– by village

- by participant

17. APPENDIX B: SCHEDULE OF STUDY PROCEDURES

Procedures	Visits (insert visit numbers as appropriate)					
	Day 0					
Informed consent	Day 0					
Demographics	Day 0					
Malaria history over previous 3 weeks	Day 0					
Temperature	Day 0					
Falciparum URDT (+50µL sample collection in group 1)	Day 0					
Falciparum positive participant						
Clinical examination	Day 0					
Treatment	Day 0	Day 1	Day 2	*		
Passive AE follow-up (study team/MPW)	Day 0	Day 1	Day 2	Day 3	Day 4	
All participants						
Passive incidence data collection	Day 0				Daily	Day 365
Group 1 villages						
Demographic data collection	Day 0					Day 365
M12 follow-up survey in group 1: URDT+50µL sample collection						Day 365
*a longer follow-up may be required for patients receiving specific regimen other than standard MDA treatment (DP3+sldPMQ) or standard first-line treatment for clinical cases (AL3+sldPMQ).						

